9.2 Study Drug Compliance

The treatment compliance (%) of study drug will be summarized using the mean, standard deviation, minimum, median, and maximum for safety population. The compliance rate will be calculated as follows:

Compliance rate (%) = the total number of injection received/the total number of injection expected * 100

10.0 Efficacy Analysis

10.1 General Considerations

For all efficacy endpoints, the descriptive statistics including number of observations, mean, standard deviation, minimum, median, and maximum for continuous variables; and number and percent for discrete variables, will be summarized for ITT analysis set. No statistical tests will be performed.

10.2 Primary Efficacy Analyses

The primary efficacy variable is the proportion of subjects with endoscopic improvement at Week 40 among subjects with endoscopic improvement at Week 0 of Study M14-347.

A two-sided 95% confidence interval will be calculated for ITT analysis set. Missing SES-CD at Week 40 will be imputed using non-responder imputation (NRI) approach. The LOCF method will be used as the sensitivity analyses.

10.3 Additional Efficacy Analyses

For additional efficacy endpoints, the baseline is defined as the Baseline in Study M14-115. The additional efficacy variables are listed as below.

- Proportion of subjects with CDAI remission (CDAI < 150) over time among subjects with CDAI remission at Week 0 of Study M14-347.
- Proportion of subjects with endoscopic improvement, defined as an SES-CD ≤ 4 and at least 2 point reduction versus Study M14-115 Baseline and no subscore greater than 1 in any individual variable at Week 40.
- Proportion of subjects with CDAI remission (CDAI < 150) over time.
- Proportion of subjects with CDAI < 150 at Week 40 and SES-CD ≤ 4 and at least a 2 point reduction versus Study M14-115 Baseline and no subscore greater than 1 in any individual variable at Week 40 among subjects with CDAI < 150 at Week 0 and SES-CD ≤ 4 and at least a 2 point reduction versus Study M14-115 Baseline and no subscore greater than 1 in any individual variable at Week 0 of Study M14-347.
- Proportion of subjects with CDAI < 150 at Week 40 and SES-CD ≤ 4 and at least a 2 point reduction versus Study M14-115 Baseline and no subscore greater than 1 in any individual variable at Week 40.
- Proportion of subjects with endoscopic response at Week 40 among subjects with endoscopic response at Week 0 of Study M14-347.
- Proportion of subjects with endoscopic response at Week 40.
- Change from Study M14-115 Baseline in fecal calprotectin level over time.

- Proportion of subjects with hs-CRP < 5 mg/L and fecal calprotectin < 250 µg/g over time among subjects with hs-CRP < 5 mg/L and fecal calprotectin < 250 µg/g at Week 0 of Study M14-347.
- Proportion of subjects with hs-CRP < 5 mg/L and fecal calprotectin < 250 µg/g over time.
- Proportion of subjects with CDAI < 150, hs-CRP < 5 mg/L, and fecal calprotectin < 250 µg/g over time among subjects with CDAI < 150, hs-CRP < 5 mg/L, and fecal calprotectin < 250 µg/g at Week 0 of Study M14-347.
- Proportion of subjects with CDAI < 150, hs-CRP < 5 mg/L, and fecal calprotectin < 250 µg/g over time.
- Proportion of subjects with CDAI < 150, hs-CRP < 5 mg/L, SES-CD \leq 4 and at least 2 point reduction versus Study M14-115 Baseline and no subscore greater than 1 in any individual variable, and fecal calprotectin < 250 µg/g at Week 40 among subjects with CDAI < 150, hs-CRP < 5 mg/L, SES-CD \leq 4 and at least 2 point reduction versus Study M14-115 Baseline and no subscore greater than 1 in any individual variable, and fecal calprotectin < 250 µg/g at Week 0 of Study M14-347.
- Proportion of subjects with CDAI < 150, hs-CRP < 5 mg/L, SES-CD \leq 4 and at least 2 point reduction versus Study M14-115 Baseline and no subscore greater than 1 in any individual variable, and fecal calprotectin < 250 µg/g at Week 40.
- Proportion of subjects with SES-CD \leq 2 at Week 40 among subjects with SES-CD \leq 2 at Week 0 of Study M14-347.
- Proportion of subjects with SES-CD \leq 2 at Week 40.
- Proportion of subjects with CDAI response (decrease in CDAI \geq 70 points from Study M14-115 Baseline) over time among subjects with CDAI response at Week 0 of Study M14-347.
- Proportion of subjects with CDAI response (decrease in CDAI \geq 70 points from Study M14-115 Baseline) over time.
- Proportion of subjects with enhanced CDAI response (decrease in CDAI \geq 100 points from Study M14-115 Baseline) over time among subjects with enhanced CDAI response at Week 0 of Study M14-347.

- Proportion of subjects with enhanced CDAI response (decrease in CDAI ≥ 100 points from Study M14-115 Baseline) over time.
- Change in IBDQ from Study M14-115 Baseline over time.
- Proportion of subjects who discontinue corticosteroid use at each visit among subjects who used corticosteroids at Week 0 of Study M14-347.
- Proportion of subjects who achieve CDAI remission and discontinue corticosteroid use at each visit among subjects who used corticosteroids at Week 0 of Study M14-347.
- Proportion of subjects with a SFPS remission (SFPS < 50) over time among subjects with SFPS remission at Week 0 of Study M14-347.
- Proportion of subjects with a SFPS remission (SFPS < 50) over time.
- Proportion of subjects with a SFPS remission (SFPS < 50) over time among subjects with SFPS ≥ 100 at Week 0 of Study M14-347.
- Proportion of subjects with SES-CD ≤ 3 and at least 2 point reduction versus Study M14-115 Baseline and no subscore greater than 1 in any individual variable at Week 40 among subjects with SES-CD ≤ 3 and at least 2 point reduction versus Study M14-115 Baseline and no subscore greater than 1 in any individual variable at Week 0 of Study M14-347.
- Proportion of subjects with SES-CD ≤ 3 and at least 2 point reduction versus Study M14-115 Baseline and no subscore greater than 1 in any individual variable at Week 40
- Proportion of subjects with SES-CD = 0 at Week 40 among subjects with SES-CD = 0 at Week 0 of Study M14-347.
- Proportion of subjects with SES-CD = 0 at Week 40.
- Proportion of subjects with a decrease of SES-CD ≥ 3 points from Study M14-115 Baseline at Week 40 among subjects with a decrease of SES-CD ≥ 3 points from Study M14-115 Baseline at Week 0 of Study M14-347.
- Proportion of subjects with a decrease of SES-CD ≥ 3 points from Study M14-115 Baseline at Week 40.
- Proportion of subjects with a decrease in SES-CD $> 50\%$ from Study M14-115 Baseline (or for subjects with an SES-CD of 4 at Study M14-115 Baseline, at least a 2-point reduction from Study M14-115 Baseline) at Week 40 among

subjects with a decrease in SES-CD > 50% from Study M14-115 Baseline (or for subjects with an SES-CD of 4 at Study M14-115 Baseline, at least a 2-point reduction from Study M14-115 Baseline) at Week 0 of Study M14-347.

- Proportion of subjects with a decrease in SES-CD > 50% from Study M14-115 Baseline (or for subjects with an SES-CD of 4 at Study M14-115 Baseline, at least a 2-point reduction from Study M14-115 Baseline) at Week 40.
- Change from Study M14-115 Baseline in hs-CRP level over time.
- Proportion of subjects with Inflammatory Bowel Disease Questionnaire (IBDQ) response (decrease \geq 16 points from Study M14-115 Baseline) over time among subjects with Inflammatory Bowel Disease Questionnaire (IBDQ) response (decrease \geq 16 points from Study M14-115 Baseline) at Week 0 of Study M14-347.
- Proportion of subjects with Inflammatory Bowel Disease Questionnaire (IBDQ) response (decrease \geq 16 points from Study M14-115 Baseline) over time.
- Proportion of subjects with IBDQ remission (IBDQ \geq 170 points) over time among subjects with IBDQ remission (IBDQ \geq 170 points) at Week 0 of Study M14-347.
- Proportion of subjects with IBDQ remission (IBDQ \geq 170 points) over time.
- Change in WPAI from Study M14-115 Baseline over time.
- Change in European Quality of Life 5 Dimensions (EQ-5D) from Study M14-115 Baseline over time.
- Change in CDAI from Study M14-115 Baseline over time.
- Change in SFPS from Study M14-115 Baseline over time.
- Change in Abdominal Pain Rating Scale score from Study M14-115 Baseline over time.
- Change in each CDAI component subscore (number of liquid or very soft stools, abdominal pain rating, general well-being, CD related complications, anti-diarrhea use, abdominal mass, hematocrit, body weight) from Study M14-115 Baseline over time.
- Time to first dose escalation.

- Proportion of subjects who require weekly dosing at Week 1 of Study M14-347.
- Proportion of subjects with major CD related event (e.g., hospitalization, bowel surgery, abscess drainage).
- Proportion of subjects with CD related hospitalization.
- Proportion of subjects with CD related surgery.
- Proportion of subjects requiring dose escalation to weekly dosing during this study.
- Proportion of subjects with no draining fistulas over time among subjects with draining fistula at Study M14-115 Baseline.
- Proportion of subjects in each treatment group with > 50% reduction from Baseline of Study M14-115 in the number of draining fistulas over time among subjects with draining fistula at Study M14-115 Baseline.
- Resolution of extraintestinal manifestations over time.
- Proportion of subjects who achieve symptomatic remission, defined as average daily stool frequency ≤ 1.5 (and not worse than Study M14-115 Baseline) and average daily abdominal pain ≤ 1.0 (and not worse than Study M14-115 Baseline) over time among subjects with Study M14-115 Baseline average daily stool frequency ≥ 2.5 or average daily abdominal pain ≥ 2.0 .
- Proportion of subjects who achieve symptomatic remission, defined as average daily stool frequency ≤ 2.8 (and not worse than Study M14-115 Baseline) and average daily abdominal pain ≤ 1.0 (and not worse than Study M14-115 Baseline) over time among subjects with Study M14-115 Baseline average daily stool frequency ≥ 4.0 or average daily abdominal pain ≥ 2.0 .
- Proportion of subjects who achieve symptomatic response, defined as average daily stool frequency at least 30% reduction from Study M14-115 Baseline and average daily abdominal pain not worse than Study M14-115 Baseline or average daily abdominal pain at least 30% reduction from Study M14-115 Baseline and average daily stool frequency not worse than Study M14-115 Baseline, over time.

For categorical additional efficacy endpoints, the two-sided 95% confidence interval for the proportions will be provided. The NRI method will be used for subjects with missing data at the time point evaluated. The LOCF method will also be used as the sensitivity analyses.

For continuous additional efficacy endpoints, change from Study M14-115 Baseline will be summarized by descriptive statistics using mean, standard deviation, minimum, median and maximum. Both LOCF and observed case analyses will be performed.

For time to event additional efficacy endpoints, the number of event and the 25th, median, and 75th percentiles of time to event will be estimated by the product limit method. The 95% CI for the median time-to-event will also be provided if applicable.

The time to first occurrence of event will be calculated as (first occurrence of event date or censoring date – date of first dose of the treatment during this study + 1). Subjects who did not experience the event prior to discontinue or complete the study will be censored at the date the last assessment was taken. For the endpoint of time to dose escalation, subjects without experiencing an event will be censored at the last available dose date.

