5.0 Investigational Plan

5.1 Overall Study Design and Plan: Description

This is a Phase 3, multicenter, open-label extension (OLE) study which comprises a 40-week open-label period designed to evaluate the long-term efficacy, safety, and tolerability of adalimumab. Approximately 300 adult subjects who participated and successfully completed Study M14-115 and who meet all of the inclusion criteria and none of the exclusion criteria will be eligible to enroll into this study.

Subjects will be evaluated for entry into Study M14-347 at the final study visit (Week 12) of Study M14-115. A subject's participation in the study is anticipated to be up to 40 weeks. There is a \pm 3-day window for all study visits. An effort will be made to bring the subject back to their original study visit (calculated from Week 0) if they are out of the visit window.

Study visits for clinical and safety assessments will be performed at Weeks 0, 8, 16, 24, 32 and 40/Premature Discontinuation (PD). All subjects will be provided with a paper subject diary in which they will record CD-related symptoms (number of liquid or very soft stools, abdominal pain rating, general well-being) and adalimumab dosing information throughout the study. Blood samples will be collected at various time points for routine labs, along with hs-CRP, adalimumab serum concentrations, anti-adalimumab

antibody (AAA) levels and other biomarker analyses. In addition, stool samples for calprotectin and microbiota will be collected. The stool samples should be taken before starting bowel preparations for endoscopy. Endoscopic evaluation will be performed at Week 40/PD, if the PD occurs after Week 24. CDAI evaluations will be calculated based on entries recorded into the subject's diary at all study visits. The SFPS (Stool [liquid/soft] Frequency + Abdominal Pain Score) will be calculated using the weighted values for the CDAI components "Number of liquid or very soft stools" and "Abdominal pain."

The Week 12 visit of Study M14-115 will be considered Week 0 (Baseline) of Study M14-347. All subjects will receive open-label adalimumab 40 mg every other week (eow) beginning at Week 0. No dose will be administered at Week 40. Subjects may be escalated to adalimumab 40 mg every week (ew) at or after Week 1 should the subject meet the criteria for inadequate response ([Table 1](#)).

Table 1. Inadequate Response

Response Type	Definition

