Subjects may discontinue adalimumab treatment at any time during study participation (Section 5.4). Subjects will be discontinued from the study if they withdraw consent or if they are deemed unsuitable to continue for any reason by the Investigator. Subjects who end study participation early will have a PD visit. All subjects will have a follow-up phone call approximately 70 days after the last administration of study drug to obtain information on any new or ongoing adverse events (AEs). The 70-day follow-up phone call will not be required for any subject who initiates commercial adalimumab.

A schematic of the study design is presented in [Figure 2](#).

Figure 2. Study Schematic

*Week 12 from M14-115

**Dose adjustment (see figure 1) can occur at Week 2 or any time thereafter if criteria for Inadequate response are met.

Clinical evaluation will be completed at each study visit. See activities outlined in [Table 2](#).

Throughout the study, subjects will only be allowed to change the dosage of CD-specific concomitant medications as specified below:

- Immunosuppressant doses may be decreased or terminated in the event of moderate-to-severe treatment-related toxicities.
- Subjects who are taking corticosteroid therapy at Baseline of Study M14-115 should continue the steroid taper initiated during Study M14-115. Increases in steroid doses back to the dose used at Baseline of Study M14-115 to manage inadequately controlled CD-related symptoms may be undertaken at the Investigator's discretion in subjects who are receiving adalimumab 40 mg ew. For subjects taking adalimumab 40 mg eow, adalimumab dose escalation

(for subjects who meet inadequate response criteria) should be considered in lieu of increases in the steroid dose.

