5.3.3.2 Additional Efficacy Variables

For additional efficacy endpoints, the baseline is defined as the Baseline in Study M14-115.

- Proportion of subjects with CDAI remission (CDAI $<$ 150) at Week 40 among subjects with CDAI remission at Week 0 of Study M14-347.
- Proportion of subjects with a SFPS remission (SFPS $<$ 50) at Week 40 among subjects with SFPS remission at Week 0 of Study M14-347.
- Proportion of subjects who achieve CDAI remission (CDAI $<$ 150) over time.
- Time in CDAI remission (CDAI $<$ 150) for subjects in CDAI remission at Week 0 of Study M14-347.
- Time to achieve CDAI remission (CDAI $<$ 150) for subjects who were not in CDAI remission at Week 0 of Study M14-347.
- Time to first dose escalation.

- Proportion of subjects who require weekly dosing at Week 1 of Study M14-347.
- Time to achieve SFPS remission (SFPS < 50) for subjects who were not in SFPS remission at Week 0 of Study M14-347.
- Time in SFPS remission (SFPS < 50) among subjects with SFPS remission at Week 0 of Study M14-347.
- Proportion of subjects who achieve a Simplified Endoscopic Score for Crohn's Disease (SES-CD \leq 4) with an Ulcerated Surface subscore no greater than 1 in any segment at Week 40.
- Proportion of subjects who achieve a SFPS < 50 over time.
- Proportion of subjects who entered Study M14-347 who were taking corticosteroids at Week 0 of Study M14-115 who discontinue corticosteroid use and achieved CDAI remission (CDAI < 150) at Week 40.
- Proportion of subjects who entered Study M14-347 who were taking corticosteroids at Week 0 of Study M14-115 who discontinue corticosteroid use at each visit.
- Proportion of subjects with CDAI response (decrease in CDAI \geq 70 points from Baseline) over time.
- Proportion of subjects with enhanced CDAI response (decrease in CDAI \geq 100 points from Baseline) over time.
- Proportion of subjects with endoscopic response (decrease \geq 50% SES-CD from Baseline) at Week 40.
- Proportion of subjects with Inflammatory Bowel Disease Questionnaire (IBDQ) response (decrease \geq 16 points from Baseline) over time.
- Proportion of subjects with IBDQ remission (IBDQ \geq 170 points) over time.
- Change in IBDQ from Baseline over time.
- Change from Baseline in fecal calprotectin level over time.
- Change from Baseline in hs-CRP level over time.
- Proportion of subjects with hs-CRP < 5 mg/L and fecal calprotectin < 250 μ g/g over time.

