For Study M14-347, both Roche and Abbott platform are used to measure hs-CRP. The study team has decided to use Abbott platform for CSR analysis. If hs-CRP was measured by Roche platform only, the value will be converted to Abbott equivalent by a conversion factor.

Definition of Endoscopic Improvement

SES-CD \leq 4 and at least two point reduction from Study M14-115 Baseline and no subscore > 1 in any individual variable.

Definition of CDAI Remission

CDAI $<$ 150

Definition of SFPS Remission

SFPS $<$ 50

Definition of CDAI Response

Decrease in CDAI \geq 70 points from Study M14-115 Baseline

Definition of Enhanced CDAI Response

Decrease in CDAI \geq 100 points from Study M14-115 Baseline

Definition of Endoscopic Response

Decrease in SES-CD $>$ 50% from Study M14-115 Baseline

Definition of IBDQ Response

Increase in IBDQ \geq 16 from Study M14-115 Baseline

Definition of IBDQ Remission

IBDQ \geq 170

Definition of Symptomatic Remission

Average daily stool frequency \leq 1.5 and not worse than Study M14-115 Induction baseline AND average daily abdominal pain \leq 1.0 and not worse than Study M14-115 Induction baseline.

Definition of Symptomatic Response

Average daily stool frequency at least 30% reduction from Study M14-115 Induction baseline and average daily abdominal pain not worse than Study M14-115 Induction baseline OR average daily abdominal pain at least 30% reduction from Study M14-115 Induction baseline and average daily stool frequency not worse than Study M14-115 Induction baseline.

Discontinued Corticosteroid Use at Each Visit Among Subjects Who Used Corticosteroids at Week 0 of Study M14-347

Discontinued steroid use at each visit is based on the steroid use on the date of CDAI measurement for that visit. If the subject has no CDAI for the visit, the steroid use on the nominal day for that visit ([Table 3](#)) will be evaluated.

If a subject discontinued the study, 'discontinued corticosteroid use' will be classified as No from that point through the end of the study.

If a subject met censoring criteria for CD-related concomitant therapy or dose escalation, whichever is earlier, 'discontinued steroid use' will be classified as No from that point through the end of the study.

EuroQol-5D-5L (EQ-5D)

EQ-5D is a standardized measure of health status developed by the EuroQol Group in order to provide a simple, generic measure of health for clinical and economic appraisal.

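### The SAP defines both steroid-withdrawal endpoints among corticosteroid users at M14-347 Week 0, the protocol among users at M14-115 Week 0; SAP 12.1 does not declare the change and the protocol's estimates are not produced

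*SAP*

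**What the plan says.** **Protocol.** Section 5.3.3.2, repeated in the synopsis, lists two steroid endpoints. The first is "Proportion of subjects who entered Study M14-347 who were taking corticosteroids at Week 0 of Study M14-115 who discontinue corticosteroid use at each visit". The second, assessed at Week 40, concerns entrants "who were taking corticosteroids at Week 0 of Study M14-115 who discontinue corticosteroid use and achieved CDAI remission". Both denominators are fixed at the start of the parent study.

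**SAP.** Section 10.3 lists "Proportion of subjects who discontinue corticosteroid use at each visit among subjects who used corticosteroids at Week 0 of Study M14-347" and "Proportion of subjects who achieve CDAI remission and discontinue corticosteroid use at each visit among subjects who used corticosteroids at Week 0 of Study M14-347". The derivation rule in SAP 6.0 carries the same population in its title: "Discontinued Corticosteroid Use at Each Visit Among Subjects Who Used Corticosteroids at Week 0 of Study M14-347". The M14-347 wording therefore stands in three places and is unlikely to be a slip in one bullet.

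**Timing.** Protocol 5.1 states: "The Week 12 visit of Study M14-115 will be considered Week 0 (Baseline) of Study M14-347". It also says that subjects on corticosteroids at M14-115 Baseline "should continue the steroid taper initiated during Study M14-115".

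**Declared changes.** SAP 12.1 lists endpoints dropped from and added to the protocol set. It mentions neither the steroid denominator nor the move of the composite from Week 40 to every visit.

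**The concern.** The two denominators are set 12 weeks apart, with a taper running in between, so they select different people and answer different questions. The protocol asks how many steroid-treated entrants are off steroids, and how many are in steroid-free remission at Week 40. The SAP asks how many of those still on steroids when the extension began came off later.

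The change also sits oddly within SAP 10.3. That section takes M14-115 Baseline as the baseline for additional endpoints, and the fistula endpoints keep an M14-115 Baseline denominator. Most endpoints that condition on M14-347 Week 0 status, such as CDAI remission, SFPS remission and endoscopic response, are paired with a row without that condition. The steroid endpoints have no such partner, so a programmer following the SAP would never compute the protocol's estimate.

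At stake are the meaning and precision of two reported proportions, and the traceability of an endpoint change in an open-label study. The SAP is Version 1.0 of 13 November 2017 and already describes enrolment of 252 subjects in the past tense.

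**Working it through.** The documents state no figure for these endpoints and no sample size calculation, so there is nothing to reproduce. The check compares who is counted and then gives an illustration on stated assumptions.

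**1. Who is counted**

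| Steroid status | Protocol | SAP |
|---|---|---|
| On at M14-115 Week 0, off at M14-347 Week 0 | In | Out |
| On at both | In | In |
| Not on at M14-115 Week 0, on at M14-347 Week 0 | Out | In |

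Subjects in the second row who finish the taper after M14-347 Week 0 stay in the SAP denominator and can count as successes. For the third row, SAP 6.0 scores every binary endpoint as No in M14-347 if the subject met the concomitant-therapy censoring criteria during M14-115. The documents do not say how many such subjects exist. Protocol exclusion criterion 8 (non-compliance with medication requirements in M14-115) may have kept some out.

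**2. Size of the difference**

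Let f be the share of M14-115 Week 0 users already off at M14-347 Week 0. Let s be the success rate at the assessed visit in those already off, and g the rate in those still on. Leaving the third row aside:

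- protocol rate = f × s + (1 − f) × g
- SAP rate = g
- difference = f × (s − g)

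The difference is zero if f = 0 or s = g, and changes sign if s < g. If the third row adds h subjects, all scored No, to the m still on, the SAP rate becomes g × m / (m + h).

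**3. Illustration**

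The only documented input is N = 252 (SAP 4.2). Assumed: 40% on steroids at M14-115 Week 0 (0.40 × 252 = 100.8, so 101), g = 30%, s = 60% or 80%, f = 25–75%, h = 0.

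| f | Already off / still on | Protocol rate, s = 80% | Protocol rate, s = 60% | SAP rate (n) |
|---|---|---|---|---|
| 25% | 25 / 76 | 42.4% | 37.4% | 30% (76) |
| 50% | 50 / 51 | 54.8% | 44.9% | 30% (51) |
| 75% | 76 / 25 | 67.6% | 52.6% | 30% (25) |

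For example, at f = 50% and s = 80%: (50 × 0.80 + 51 × 0.30) / 101 = 55.3 / 101 = 54.8%, a gap of 24.8 points. Directly from the formula, the extremes are 0.25 × (0.60 − 0.30) = 7.5 points and 0.75 × (0.80 − 0.30) = 37.5 points. Varying the steroid-user share from 20% to 60% (50 to 151 subjects) and rounding to whole subjects gives gaps of 7.2 to 38.0 points, and SAP denominators of 12 to 113.

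**4. Precision**

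Wald 95% half-width = 1.96 × √(p(1 − p)/n). With 101 steroid users and s = 80%, the protocol version has a half-width of 9.1 to 9.7 points. The SAP version has 10.3 points on 76 subjects, 12.6 on 51 and 18.0 on 25 (1.96 × √(0.21/25) = 0.180).

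**The case against.** The strongest reply is that the SAP's question is sensible for an extension study. Discontinuation among those still on steroids at entry isolates what happened in the extension, whereas the protocol version also credits weaning achieved under the parent study's two induction regimens. That stands as a reason to keep the SAP version. It is not a reason to replace the protocol's endpoint without saying so.

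The consequences are also limited. These are two of several dozen additional endpoints; SAP 10.1 plans no tests, SAP 10.4 treats multiplicity as not applicable, and no sample size rests on them. The move of the composite to every visit loses nothing in itself, because Week 40 is still among the visits. All of this stands.

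Three stronger readings are tempting, and the documents do not support them:

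- *The SAP removes everyone who tapered successfully.* It removes only those already off steroids at M14-347 Week 0. The taper continues into the extension, and later finishers remain.
- *The SAP population is the harder-to-wean remainder.* The M14-115 taper schedule is not given. Being on steroids at parent Week 12 may reflect starting dose or timing. The SAP population need not be a subset of the protocol's either.
- *The SAP rate is known to be much lower.* The direction and size depend on s and g, for which there is no source. The SAP also scores dose-escalated subjects as not having discontinued from the point of escalation, which can affect both rates.

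**Conclusion.** The inconsistency is certain on the text. Protocol and SAP use different denominators for both endpoints, no SAP row restores the protocol's, and SAP 12.1 does not record the change. Followed exactly, the SAP does not deliver either steroid estimate that the protocol specifies.

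The numerical effect is unknown, because the number on corticosteroids at either Week 0 is not given. The 7 to 38 points show what is plausible under assumed values of f, s and g and no new steroid starters; they are not an estimate for this trial. The primary endpoint and the safety analyses are unaffected. The point should be corrected, but its weight is that of a descriptive, additional endpoint.

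**What to change.** 1. In SAP 6.0 and 10.3, define both endpoints among M14-347 entrants taking corticosteroids at Week 0 of M14-115. The derivation in SAP 6.0 works from steroid status on the date of each CDAI, so only its population needs to change.
2. Identify Week 40 as the protocol timepoint for steroid-free CDAI remission. Reporting at other visits can stay.
3. Keep the M14-347 Week 0 users as a supplementary row, labelled as such.
4. Record the supplementary population and the each-visit reporting of the composite in SAP 12.1, with the reason.

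The cost is SAP wording and one extra table row per endpoint. No new data are needed: SAP 7.1 and 7.3 already summarise steroid use at M14-115 Baseline, and the censoring rule in SAP 6.0 already needs the M14-115 Baseline dose. No clinical rule is touched.
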